5.10 Procedures Related to Discharge

568 Parent/guardian(s) will show proficiency of using the system before leaving for the home portion
569 of the trial.

571 Parent/guardian(s) will show proficiency on how to change CGM before leaving for the home use
572 portion of the trial.

573 The child participant's SMBG value needs to be between 70-300 mg/dL and ketone concentration
574 is ≤ 0.6 mmol/L prior to discharge. The parent/guardian(s) and child will be offered a snack prior
575 to discharge. The study team will verify that parent/guardian(s) have study team's contact
576 information.

577 **Chapter 6: CONTROL-IQ AT HOME**

578 **6.1 At-Home Use**

579 Child participants will continue to use the Control-IQ System for another 72 hours at home under
580 parental/legal guardian(s) supervision. The study team will continue remote monitoring as
581 described in section 8.2. Study staff will be available 24/7 by phone to answer any questions or
582 concerns or to help resolve any technical problems.

583 At the conclusion of 72 hours, the parent/guardian(s) will remove the study equipment under the
584 supervision of a study physician which may occur at home or in the presence of study staff.
585 Participants who discontinue use of the study devices at home will return study devices by standard
586 shipping (e.g. FedEx) provided by the research team.

587 Parent/guardian(s) will be asked to download the child participant's personal pump to ensure the
588 child's personal equipment is working properly.

589 **6.2 Meal Bolus**

590 Child participants may consume meals and snacks of their own choice with no restrictions. Meal
591 size will be estimated by the parent/guardian(s). The timing of the bolus will be per each child
592 participant's typical dosing routine.

593 **6.3 Blood Glucose Checks**

594 Parent/guardian(s) will be advised to obtain their child's fingerstick blood glucose value prior to
595 bedtime each night of at-home use.

596 **6.4 Activity**

597 The child should refrain from activity (e.g. sports) if their CGM value is below 90 mg/dL.

598 **6.5 Caregivers**

599 In the event that the child is in the care of someone other than the parent/guardian(s), the child
600 must be routinely cared for by this individual (i.e. more than once per week for more than one
601 month). This individual must be trained on the use of the study devices and safety guidelines by
602 study staff prior to the child using the device at home.

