637 **7.2.1 CGM Measurements**

638 CGM values are updated every 5 minutes and parents will be able to see it on the pump and
639 Dexcom App.

640 CGM alarms on the study team controlled Dexcom App will be set at 70 mg/dL for 30 minutes and
641 300 mg/dL for 60 minutes.

642 If CGM < 80 mg/dL during the day, the patient will be treated until CGM reads >80 mg/dL. If
643 CGM < 70 mg/dL during the night. Hypoglycemia treatment will be provided until CGM reads $>$
644 80 mg/dL. SMBG may be performed if the MD on-call deems it necessary.

645 If CGM >300 mg/dL for more than 60 minutes, SMBG will be performed every 60 minutes. If
646 SMBG >300 mg/dL, the Glycemic Treatment Guidelines will be applied.

647 A study team member will contact the family if either of the above conditions is triggered and
648 confirm treatment per provided guidelines.

649 **7.2.2 Ketone Measurements**

650 Parent/guardian(s) will be advised to test for ketones any time the CGM is above 300 mg/dL for
651 more than 2 hours.

652 If ketones are 0.6-3.0 mmol/L, the following guidelines should be followed until SMBG < 250
653 mg/dL.

- 654 • Notify MD as soon as possible
- 655 • Consider taking correction dose of insulin by syringe or pen
- 656 • Change insulin in reservoir and tubing and change pump site
- 657 • Drink sugar-free beverages
- 658 • Once BG is 100-250 mg/dL, restart pump treatment in appropriate mode. Record the
659 amount of insulin that was given when prompted

660 If ketones are >3.0 mmol/L, the following guidelines should occur:

- 661 • The participant will stop the study
- 662 • Notify MD as soon as possible
- 663 • Disconnect the STUDY insulin pump and start HOME insulin pump once instructed by
664 MD
- 665 • Take correction dose of insulin by syringe or pen
- 666 • Drink sugar-free beverages

667 **Chapter 8: REMOTE MONITORING**

668 **8.1 Hotel Admission Monitoring**

669 Parent/guardian(s) will remotely monitor the subjects in real-time using the DexCom G6 App
670 capabilities provided by Dexcom® Inc. during the Hotel Admission.

671 Staff will remotely monitor the subjects in real-time using the DexCom G6 capabilities provided
672 by Dexcom® Inc. . Notification will be set for CGM readings below 80mg/dl during the day and
673 70mg/dl at night or above 250mg/dl to alert study staff of the need treatment or SMBG
674 confirmation. In case of remote monitoring failure, CGM alarms will be activated at low=70

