675 mg/dL and high=250 mg/dL for the study personnel to act if alarms are set off.

676 **8.2 Home Monitoring**

677 Parent/guardian(s) will remotely monitor the subjects in real-time using the DexCom G6 App
678 capabilities provided by Dexcom® Inc. Alerts will be setup for values below 70mg/dL and above
679 250mg/dL; families may choose to use more conservative thresholds (i.e. higher than 70 and/or
680 lower than 250) as well as supplemental alerts.

681 Additionally, a smart phone with the Dexcom Share app will always be in the vicinity of the child
682 during the home study. This app may be on a parent's phone or the study team will provide a
683 phone that will be used with parents or caretakers.

684 In addition, the study staff will include the staff remote monitoring for threshold alerts but with
685 alerts adapted to the existence of a first tier remote monitor (parent/legal guardian(s)) and the fact
686 that they are not one site. Therefore, the study staff (Tier 2) alerts will be <70mg/dL for more than
687 15 minutes and >300 mg/dL for more than 60 minutes.

688 **Chapter 9: TESTING PROCEDURES**

689 **9.1 Laboratory / Point of Care Testing**

690 **9.1.1 HbA1c**

691 • Performed locally at the Screening visit. Blood test may be obtained within 30 days prior
692 to enrollment.

693 • HbA1c level will be measured using the DCA Vantage Analyzer, a comparable point of
694 care device or local laboratory

695

696 **Chapter 10: RISKS ASSOCIATED WITH CLINICAL TRIAL**

697 **10.1 Potential Risks and Benefits of the Investigational Device**

698 Risks and Benefits are detailed below. Loss of confidentiality is a potential risk; however, data are
699 handled to minimize this risk. Hypoglycemia, hyperglycemia and ketone formation are always a
700 risk in participants with type 1 diabetes and participants will be monitored for these symptoms.

701 **10.1.1 Known Potential Risks**

702 **10.1.1.1 Venipuncture Risks**

703 A hollow needle/plastic tube will be placed in the arm for taking blood samples. Blood draws can
704 cause some common reactions like pain, bruising, or redness at the sampling site. Less common
705 reactions include bleeding from the sampling site, formation of a small blood clot or swelling of
706 the vein and surrounding tissues, and fainting.

707 **10.1.1.2 Fingerstick Risks**

708 About 1 drop of blood will be removed by fingerstick for measuring blood sugars and sometimes

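### Section 7.2.2 lets the home steps for ketones of 0.6-3.0 mmol/L end, and Control-IQ resume, on glucose alone, with no repeat ketone test

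*Combined protocol and SAP*

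**What the plan says.** Section 7.2.2 sets the home ketone rules. The trigger is glucose-based: "Parent/guardian(s) will be advised to test for ketones any time the CGM is above 300 mg/dL for" more than 2 hours. For the middle band, "If ketones are 0.6-3.0 mmol/L, the following guidelines should be followed until SMBG < 250" mg/dL. The steps are to notify the MD, consider a correction dose by syringe or pen, replace the insulin, tubing and infusion site, and give sugar-free drinks. The last step is "Once BG is 100-250 mg/dL, restart pump treatment in appropriate mode". No repeat ketone measurement is listed.

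Above 3.0 mmol/L the child stops the study, and the instruction is "Disconnect the STUDY insulin pump and start HOME insulin pump once instructed by" the MD.

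The two hotel checks are worded differently. At discharge (5.10) the child's "SMBG value needs to be between 70-300 mg/dL and ketone concentration" "is ≤ 0.6 mmol/L prior to discharge". On arrival (7.1) the child continues only once CGM is 70-300 mg/dL and ketones are at most 0.6 mmol/L.

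Home monitoring includes staff alerts at CGM below 70 mg/dL for more than "15 minutes and >300 mg/dL for more than 60 minutes" (8.2). Section 7.2.1 starts hourly fingersticks once CGM has been above 300 mg/dL for more than 60 minutes, and says "A study team member will contact the family if either of the above conditions is triggered and" confirm treatment.

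**The concern.** The middle band opens on a ketone value but closes on a glucose value. At arrival and discharge, where staff are present, the protocol does not accept glucose alone as evidence that a child is fit to proceed. At home, after a reading already known to be raised, it does.

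Once glucose has fallen, the only home test trigger no longer applies. A later value above 3.0 mmol/L, the protocol's own stop level, would be found only if the MD or staff asked for a test, the family chose to test, or glucose climbed back above 300 mg/dL for more than 2 hours.

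The primary aim is the safety profile (1.3). Section 10.1.1.5 names ketonemia as a risk when insulin is attenuated or suspended for an extended period, or when the pump or infusion set is not working. Part of the band is also reportable under 11.1.2.2: 1.5 mmol/L or more once a health care provider has been contacted, and 3.0 mmol/L even without contact. A second reading is the direct check that the correction and set change worked, and the plan does not require one.

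**Working it through.** There is no planned figure to reproduce. The check sets the rules side by side.

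| Decision point | Glucose condition | Ketone condition |
|---|---|---|
| Arrival, continue (7.1) | CGM 70-300 mg/dL | at most 0.6 mmol/L |
| Discharge (5.10) | SMBG 70-300 mg/dL | at most 0.6 mmol/L |
| Home, end of steps after 0.6-3.0 mmol/L (7.2.2) | SMBG below 250 mg/dL | none |
| Home, pump restart after 0.6-3.0 mmol/L (7.2.2) | BG 100-250 mg/dL | none |

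The arrival row rests on 7.1. Section 5.4 also covers check-in, but its ketone wording appears inverted (it prompts corrective action at 0.6 mmol/L or below), so it is used only for its pointer to 7.1.

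No other section supplies the missing test:
- 4.3.2 sends the reader back to 7.2.
- 6.3 asks for a bedtime fingerstick glucose only.
- 6.6 verifies that ketone data were collected, about 48 hours after home use ends.
- 8.2 sets glucose alerts only.
- 11.1.6 follows unresolved reported events, but gives no ketone value when the steps end.

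Timing of staff contact: the staff alert comes at more than 60 minutes above 300 mg/dL, and the ketone test at more than 2 hours. Staff should therefore be in touch before the first ketone value.

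Exposure: 15 children (the planned maximum) × 72 h = 1,080 h; 1,080 / 24 = 45 child-days at home.

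Room for lost closed-loop time, as a break-even and not an estimate. Section 13.2.3 counts a home session if at least 56 h of closed loop are completed.
- Slack: 72 - 56 = 16 h.
- After injected insulin, 4.1.1 already takes Control-IQ off for about 4 h: 16 - 4 = 12 h left. Those 4 h are not a cost of the change proposed here.

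**The case against.** The strongest reply is that a physician and staff are already involved. Staff are alerted and contact the family, the MD is notified, the set and insulin are replaced, families carry the ketone meter (Chapter 4), and staff can be reached by phone at all hours (6.1). Arrival and discharge are routine checks at supervised transitions, whereas this is treatment of a known event. The branch above 3.0 mmol/L lists no recheck either. If the correction fails and CGM stays or returns above 300 mg/dL for 2 hours, the test trigger applies again.

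Most of this stands as mitigation. It leaves a narrower gap: a child whose glucose has fallen, with the MD notified, and no ketone value required before the steps close. None of the safeguards requires a recheck. The upper branch also differs, because there the home pump starts only on the MD's instruction and the child leaves the study; in the middle band the MD is only notified.

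Stronger readings are tempting and the documents do not support them:
- A reader might infer that restarting the pump on glucose is itself the error. It is not; prompt pump insulin should be kept.
- A reader might infer that ketones would rise after restart, or that Control-IQ is less safe than open loop with residual ketones. The documents show neither.
- A reader might treat 3.0 / 0.6 = 5, or 300 - 250 = 50 mg/dL, as measures of risk. The first is a ratio of protocol limits. The second subtracts a fingerstick limit from a CGM limit.

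**Conclusion.** The point holds as a cheap improvement to a safety rule. Followed as written, 7.2.2 allows a ketone reading of up to 3.0 mmol/L to be closed, and Control-IQ to resume, with no check that ketones have come down to the 0.6 mmol/L that 7.1 and 5.10 require. MD notification and staff contact reduce the gap but do not close it.

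Confidence is high that the retest is absent from the text. The size of the consequence is unknown: the documents give no rate of home ketone events, and exposure is at most 45 child-days. No effect on the primary outcome is claimed. The conclusion assumes only that families and staff follow 7.2.2 as written; an MD who routinely asks for a retest would close the gap in practice, but the protocol does not make that a rule.

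**What to change.** In 7.2.2, for the 0.6-3.0 mmol/L branch, replace the closing step with the following. Once BG is 100-250 mg/dL, restart pump insulin without delay with Control-IQ off, unless the study MD directs otherwise, and repeat the ketone test.
- At 0.6 mmol/L or below: end the ketone steps and resume Control-IQ. If insulin was given by syringe or pen, resume only after the approximately four hours in 4.1.1. This condition must be mandatory, because an unqualified return to Control-IQ would contradict 4.1.1.
- Above 0.6 and up to 3.0 mmol/L: continue the steps and call the study MD, who decides the mode and the time of the next test.
- Above 3.0 mmol/L: follow the existing stop branch.

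Remove the sentence that ends the steps on SMBG alone. The cut-offs are the protocol's own. The cost is a few lines of text, one or more ketone strips per event with the meter and strips already supplied (4.3.2), and possibly some hours less closed loop. Control-IQ can be off for up to 16 h in total before a home session falls below 56 h, or about 12 h beyond the 4.1.1 period after an injected dose, assuming no other time is lost.

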115	CHAPTER 12: MISCELLANEOUS CONSIDERATIONS.....	45
116	12.1 Prohibited Medications, Treatments, and Procedures	45
117	12.2 Participant Withdrawal.....	45
118	12.3 Confidentiality.....	45
119	CHAPTER 13: STATISTICAL CONSIDERATION	46
120	13.1 Statistical and Analytical Plans	46
121	13.2 Statistical Hypotheses	46
122	CHAPTER 14: DATA COLLECTION AND MONITORING	48
123	14.1 Case Report Forms and Device Data	48
124	14.2 Study Records Retention.....	48
125	14.3 Protocol Deviations	48
126	CHAPTER 15: ETHICS/PROTECTION OF HUMAN PARTICIPANTS	49
127	15.1 Ethical Standard	49
128	15.2 Institutional Review Boards	49
129	15.3 Informed Consent Process.....	49
130		

Protocol Summary

PARTICIPANT AREA	DESCRIPTION
Title	Safety of the Tandem t:slim X2 with Control-IQ Automated Insulin Delivery System in Preschoolers, age 2-6 Years Old.
Investigational Device	Tandem Control-IQ with G6 Continuous Glucose Monitor
Objectives	To assess study the safety profile of the Tandem t:slim X2 with Control-IQ system in children with T1D aged 2-6 years old under free living condition
Study Design	A single-arm, multi-center, clinical study
Number of Sites	3 independent clinical sites – sharing IDE and regulatory documentation only
Endpoint	Number of subjects with less than 6% time below 70 mg/dL and less than 40% time above 180 mg/dL.
Population	
Key Inclusion Criteria
 
 • Age ≥ 2 and < 6 years old at the time of visit 1 • Clinical diagnosis, based on investigator assessment, of type 1 diabetes for at least 3 months and using insulin at the time of enrollment • Use of an insulin pump in the past 3 months • Use of Dexcom G6 for at least 11 out of the last 14 days 
Key Exclusion Criteria
 
 • Hypoglycemia induced seizure or loss of consciousness in the past 3 months • Concurrent use of any non-insulin glucose-lowering agent • A condition, which in the opinion of the investigator or designee, would put the participant or study at risk.
Sample Size	Up to 15 participants
Participant Duration	About 14 days
Protocol Overview/Synopsis	48 hour hotel stay with 24/7 study team supervision followed by parental remote monitoring for 72 hours of at-home use

Study Visits and Procedures Schedule

	SCREENING	OPEN LOOP AT-HOME USE	PRE- ADMISSION CHECK-IN	HOTEL ADMISSION	CLOSED LOOP AT- HOME USE	POST- ADMISSION CHECK-IN
DURATION	ABOUT 3 HOURS		ABOUT 30 MINUTES	ABOUT 48 HOURS	ABOUT 72 HOURS	ABOUT 30 MINUTES

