451 to use in order to collect the data from the devices.

452 **4.3 Blood Glucose and Ketone Testing**

453 **4.3.1 Blood glucose testing**

454 Parent/guardian(s) will be provided with a study blood glucose meter and test strips to be used at
455 home per manufacturer guidelines.

456 All study blood glucose meters will be QC tested by study staff with at least two different
457 concentrations of control solution, if available. A tested meter will not be used in a study if it does
458 not read within the target range at each concentration per manufacturer labeling.

459 Parent/guardian(s) will be reminded to use the study blood glucose meter for all fingerstick BGs
460 during the study.

461 **4.3.2 Blood ketone testing**

462 Parent/guardian(s) will be provided with a study blood ketone meter and test strips to be used at
463 home per manufacturer guidelines.

464 All study blood ketone meters will be QC tested by study staff with at least two different
465 concentrations of control solution, if available. A tested meter will not be used in a study if it does
466 not read within the target range at each concentration per manufacturer labeling.

467 Parents/legal guardian(s) will be instructed to perform blood ketone testing as described in
468 Glycemic Treatment Guidelines (section 7.2). A home glucagon emergency kit will be required.
469 Participants who currently do not have one will be given a prescription for the glucagon emergency
470 kit.

471 **4.4 Optimization of Insulin Pump Settings**

472 Data-driven optimization of pump settings can occur any time during the study, particularly if the
473 parent/guardian(s) contacts the study physician due to concerns about their pump settings due to
474 recurring hypo- or hyperglycemia.

475 **Chapter 5: HOTEL ADMISSION PROCEDURES**

476 **5.1 General Admission Instructions**

477 The Hotel Admission will take place in a hotel or research house for approximately 48 hours.
478 Alternately, the clinical trial may occur at a house.

479 The CGM used in the study is FDA-approved for the non-adjunctive measurement of blood
480 glucose (i.e. the CGM reading can be used for insulin dosing decisions). The CGM readings will
481 be the primary source of blood glucose levels. There are no protocol fingerstick blood glucose
482 measurements other than at times of CGM calibration (if necessary) and if directed by the study

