1068 Participation in the study is voluntary, and a participant may withdraw at any time. For participants
1069 who withdraw, their data will be used up until the time of withdrawal.

1070 **12.3 Confidentiality**

1071 For security and confidentiality purposes, subjects will be assigned an identifier that will be used
1072 instead of their name. Protected health information gathered for this study may be shared with the
1073 third party collaborators. De-identified subject information may also be provided to collaborators
1074 involved in the study after the appropriate research agreement has been executed.

1075 **Chapter 13: STATISTICAL CONSIDERATION**

1076 **13.1 Statistical and Analytical Plans**

1077 This trial is single-armed and not powered to detect differences between groups. The study is
1078 designed to obtain a primary safety profile on patients in this age-group.

1079 This study is an early feasibility study that will test the safety of t:slim X2 with Control-IQ
1080 Technology in an outpatient setting. These studies would generate up to 75 days of closed-loop
1081 data. This sample size allows for subject withdrawal.

1082 **13.2 Statistical Hypotheses**

1083 **13.2.1 Primary Outcome**

1084 Number of subject with less than 6% time below 70mg/dL and less than 40% time above
1085 180mg/dL.

1086 **13.2.2 Secondary Outcome**

- 1087 1. % time spent <70 mg/dl, <60mg/dl, <54mg/dL, and <50mg/dL
- 1088 2. % time spent >180mg/dl, and >250mg/dl, >300 mg/dl
- 1089 3. % time spent between 70-180mg/dl
- 1090 4. % time spent between 70-150mg/dl
- 1091 5. Number of hypoglycemia below 70 mg/dL
- 1092 6. Number of carbohydrate treatments, as well as total amount of carbohydrates used for
1093 treatments.
- 1094 7. Time spent in closed loop
- 1095 8. Time with available CGM
- 1096 9. Number of subject with more than 70% time in 70-180mg/dL range with less than 4%
1097 time below 70mg/dL

1098 **13.2.3 Success Criteria / Goal**

1099 As a general rule, a session will be considered useful for data analysis if the subject completes
1100 close to 80% of the active study protocol. Sessions are considered separate: (i) Supervised
1101 Phase=complete at least 38 hours of AP; (ii) at home use=complete at least 56 hours of AP.

1102 *The primary goal will be considered met if the primary outcome is achieved for 65% or more of
1103 the subjects.*

1104 **13.2.4 Statistical Analysis Plan**

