1105 Proportions of subject matching primary criteria will be computed and directly compared to 65%
1106 (considered baseline). Further analysis will be performed using a chi² test of goodness of fit. Based
1107 on prior data in 6-12 year olds we anticipate a possible effect size of 0.64, which would allow to
1108 detect a difference with 70% power considering our sample size.

CLINICAL PROTOCOL

1109 Overall outcomes will be compared to the normative data below (values derived from the analysis
1110 of 30 6-12 year old T1D subjects using pumps and CGM and rounded for ease of use):

	Baseline	
	mean	std
% time below 50mg/dL	0.5%	0.5%
% time below 54mg/dL	1%	0.8%
% time below 60mg/dL	2%	1%
% time below 70 mg/dL	4%	2.5%
% time between 70-140mg/dL	40%	9%
% time between 70-180mg/dL	60%	9%
% time above 180mg/dL	35%	9%
% time above 250mg/dL	11%	5%
% time above 300mg/dL	4%	3%
Average CGM [mg/dL]	162.0	15.0

1111 This analysis will be performed using a single group one sided t-test for mean comparison for
1112 outcomes that can be assumed normally distributed and One-Sample Wilcoxon Signed Rank test
1113 for median comparison for the others, this analysis is not powered.

1114 Secondary outcomes will be reported for the entire period and for the supervised and home phases
1115 separately. Outcomes by phase will be compared to each other to assess possible loss of
1116 performances during the transition at home. For this purpose, McNemar's tests will be used to
1117 compare the supervised phase to the home phase for the primary outcome and secondary outcome
1118 # 6, 7, and 8. All other outcomes will be analyzed using repeated measure ANOVA. Significance
1119 of 0.05 will be used.

1120 This analysis is not powered.

1121 **Chapter 14: DATA COLLECTION AND MONITORING**

1122 **14.1 Case Report Forms and Device Data**

1123 The study data are collected through a combination of case report forms (electronic and paper) and
1124 electronic device data files obtained from the software and individual hardware components.
1125 These electronic device files and electronic CRFs are considered the primary source
1126 documentation.

1127 When data are directly collected in electronic case report forms, this will be considered the source
1128 data. Records will be maintained in accordance with ICH E6 and institutional regulatory
1129 requirements for the protection of confidentiality of participants.

1130 **14.2 Study Records Retention**

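### Secondary outcome 5 has no exposure denominator, so comparing a roughly 48 h hotel phase with a 72 h home phase is biased toward more hypoglycemia at home

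*Combined protocol and SAP*

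**What the plan says.** Section 13.2.2 gives outcome 5 as "Number of hypoglycemia below 70 mg/dL". No denominator is attached and no rule defines an episode. The glucose-range outcomes beside it (1 to 4) are percentages of time, for example "time spent between 70-180mg/dl", which do not grow with the length of observation.

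Section 13.2.4 reports the secondary outcomes for the whole period and for each phase, and adds: "Outcomes by phase will be compared to each other to assess possible loss of" performance on going home. McNemar's test is assigned to the primary outcome and outcomes 6, 7 and 8. Outcome 5 is not on that list, so it falls under "All other outcomes will be analyzed using repeated measure ANOVA", at a significance level of 0.05. The section states that this analysis is not powered.

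The phases differ in length by design. The Protocol Summary describes a "48 hour hotel stay with 24/7 study team supervision followed by parental remote monitoring for 72 hours of at-home use". Sections 5.1 and 6.1 agree: "The Hotel Admission will take place in a hotel or research house for approximately 48 hours" and "Child participants will continue to use the Control-IQ System for another 72 hours at home under" parental supervision. Section 13.2.3 sets the least time for a usable session: "Phase=complete at least 38 hours of AP; (ii) at home use=complete at least 56 hours of AP".

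Nowhere do the documents supply a rate, an offset or any other exposure adjustment for outcome 5.

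**The concern.** A number of events grows with the time over which events can occur. A child whose tendency to go low is the same in both places will, on average, have more events in the longer phase. The comparison is meant to detect deterioration once on-site staff supervision ends, and the longer phase is the home phase, so the built-in difference points exactly toward the finding being looked for. The same mechanism can hide a true improvement.

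Assessing safety at home is the first secondary aim (section 1.4), and outcome 5 is the only listed secondary outcome that counts hypoglycemic events. A biased result here could mislead a reader about the move from hotel to home.

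**Working it through.** **Inputs from the documents.** Up to 15 participants (Protocol Summary); hotel phase about 48 h and home phase 72 h (Protocol Summary, 5.1, 6.1); session minimums 38 h and 56 h (13.2.3); significance level 0.05 (13.2.4).

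**Check of the phase lengths.** Section 13.1 states up to 75 days of closed-loop data. 15 × (48 + 72) / 24 = 75 days, so the plan's own total uses these lengths.

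**Expected ratio of counts.** If a child's event rate is the same in both phases, expected count = rate × hours. The rate cancels, so expected home count / expected hotel count = home hours / hotel hours.

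| Hotel h | Home h | Ratio |
|---|---|---|
| 48 | 72 | 72/48 = 1.50 |
| 38 | 56 | 56/38 = 1.47 |
| 48 | 56 | 56/48 = 1.17 |
| 38 | 72 | 72/38 = 1.89 |

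The ratio exceeds 1 throughout, because the shortest usable home session (56 h) is longer than the full hotel stay (48 h). This step needs no assumption about the event rate or the test.

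**Effect on the test (assumptions needed).** The documents give no event rate, so a range was used: 0.5 to 3 events per day, identical in both phases. Each child's rate is gamma-distributed with a CV of 50%, and counts are Poisson. There are 15 children per trial. The test is a two-level repeated-measures ANOVA, which is the same as a two-sided paired t-test at 0.05. Percentage of simulated trials wrongly showing significantly more events at home:

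| Assumed events/day | Counts, 48 h vs 72 h | Counts, 48 h vs 56 h |
|---|---|---|
| 0.5 | 19% | 6% |
| 1 | 35% | 8% |
| 2 | 60% | 12% |
| 3 | 77% | 16% |

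With events per 24 h in place of counts, the false home-worse rate is about 2.5% (2.4% to 3.0%) and the two-sided error about 5%. With the between-child CV varied from 0 to 1, the 48 h vs 72 h figures for counts span about 16–20%, 29–36%, 51–63% and 67–80% at the four rates.

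**Masking.** Suppose the true rate falls by one third at home, from 2.0 to 1.33 per day. Expected counts are 2.0 × 2 days = 4.0 in the hotel and 1.33 × 3 days = 4.0 at home, so they are equal. In simulation, counts detect the fall in about 2% of trials and rates in about 49%.

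**The case against.** The case for leaving this alone has several parts.

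- **The plan is silent rather than wrong.** It says neither raw nor unadjusted, and an analyst could report events per day without contradicting it; outcome 8 even offers a denominator. That is true, but nothing requires it. Followed literally, the stated outcome and test give a biased comparison, and the scale should not be left for choice after the data are seen.
- **The analysis is declared not powered.** This excuses low sensitivity. It does not excuse an error in a known direction tested at a stated 0.05.
- **Other checks exist.** This stands. Percent time below 70, 60, 54 and 50 mg/dL is compared by phase on a scale unaffected by phase length. Adverse events and low glucose values are reviewed after home use (6.6), and the Medical Monitor reviews severe hypoglycemia (11.5). A spurious rise in outcome 5 would appear beside unchanged percent time below 70. A reader might infer that the home safety check rests on outcome 5; the documents do not support that.
- **The excess is not always 50%.** This also stands. A reader might infer at least 1.5 times, particularly from the hotel timetable (arrival at 3–5 p.m., discharge after lunch on day 3). But those times are marked approximate, discharge has no stated hour, and the accepted session minimums allow ratios below 1.5, down to 1.17.
- **The largest error rates need high event rates.** This is fair. In section 1.2, Table 1, children aged 6–10 on closed loop spent 2.8% of time below 70 mg/dL: 0.028 × 1440 = about 40 min a day. At 3 events per day that is about 13 min each, fewer than three 5-minute readings, so 77% is the least plausible figure. Younger children may differ.

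**Conclusion.** The concern holds, with limited reach. As written, outcome 5 is on the wrong scale for the hotel-versus-home comparison. An unchanged rate gives about 50% more events at home at nominal lengths, 47% more when both sessions are at their minimum, and between 17% and 89% more at the extremes. That arithmetic rests only on the plan's own hours and on reading the outcome as an unscaled count. The size of the false-positive problem rests on assumed event rates, a Poisson model and the assumed between-child variation, and should be read as a range rather than a prediction.

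One secondary outcome is affected, in a comparison with no decision rule attached. The point is worth correcting because the bias runs toward the conclusion being tested and the correction is simple.

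**What to change.** In 13.2.2, define outcome 5 as the number of episodes below 70 mg/dL per 24 h of available CGM, and state one episode rule (what starts, ends and separates episodes) that applies in both phases. In 13.2.4, use that rate for the hotel-versus-home comparison.

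For consistency, show outcome 6 per 24 h and outcomes 7 and 8 as percentages of phase hours in the by-phase tables, since they also grow with phase length when given as totals. Which test suits outcomes 6 to 8 is a separate matter.

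The cost is a few lines of wording. Time with available CGM is already collected as outcome 8, so no new data, visits or participants are needed.
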